10.2.4 Monitoring of Renal Function

There is no dose adjustment required in patients with renal impairment. However, routine assessment of renal function will be undertaken with derivation of creatinine clearance using the CKD-EPI (Chronic Kidney Disease Epidemiology Collaboration) equation¹³:

$$\text{Estimated GFR} = 141 \times \min(\text{SCR}/\kappa, 1)^\alpha \times \max(\text{SCR}/\kappa, 1)^{-1.209} \times 0.993^{\text{Age}} \times (1.018 \text{ if female} \times (1.159 \text{ if black}))$$

$\kappa = 0.7$ if female

$\kappa = 0.9$ if male

$\alpha = -0.329$ if female

$\alpha = -0.411$ if male

min = the minimum of Scr/ κ or 1

max = the maximum of Scr/ κ or 1

Scr = serum creatinine (mg/dL)

Dosing of all medications in a patient's regimen should be critically reviewed if the eGFR falls below 60ml/min/1.73m². It is recommended that Investigators follow the current local guidelines for the management of renal impairment in HIV-1-infected patients and/or reference the current EACS guidelines at: (Europeanidsclinicalociety.org/guidelinespdf/2_Non_Infectious_Co_Morbidities_in_HIV.pdf. Accessed 01Dec2010)

10.3 Protocol-specific toxicity management guidelines

10.3.1 Vorapaxar Side Effect Profile

The most common AEs associated with the use of vorapaxar sulphate (2.5mg) given once daily in patients with a history of cardiovascular disease are bleeding (including intracerebral bleeding), anaemia, depression and rash, retinal disorder and diplopia/oculomotor disturbance. The most clinically relevant are summarised below.

10.3.2 Bleeding

In the phase 3 TRA 2°P TIMI 50 (Thrombin Receptor Antagonist in Secondary Prevention of Atherothrombotic Ischemic Events) study¹² (Morrow et al), vorapaxar sulphate (2.5mg) given once daily in patients with a history of myocardial infarction or peripheral vascular disease with no history of ischaemic stroke or transient ischaemic attack saw an increase in GUSTO moderate or severe bleeding by 55% compared to the placebo arm. (GUSTO: Global Utilization of Streptokinase and Tissue Plasminogen Activator for Occluded Arteries). These bleeding events were assessed as being non-CABG related bleeds. GUSTO moderate to severe bleeding was defined as bleeding requiring transfusion of whole blood or packed red blood cells with or without haemodynamic compromise, intracranial haemorrhage or fatal bleeding.

To minimise the occurrence of bleeding events, participants with a high risk of bleeding will be excluded from this study. See section 7.1 for details.

Adverse events involving bleeding will be assessed according to the BARC definitions (see Appendix 2) for bleeding. If participants are suspected of having a clinically significant bleeding event, then a blood sample should be taken to monitor haemoglobin levels in order to classify the event according to the BARC criteria. Participants will be managed as outlined below.

10.3.2.1 BARC Type 1 Bleeding

Participants who develop a BARC type 1 adverse bleeding event should continue with the study drug. Participants experience a BARC type 1 adverse bleeding event who choose to discontinue the study drug should remain on study and continue to undergo protocol-mandated evaluations and assessments.

10.3.2.2 BARC Type 2 Bleeding

Participants who develop a BARC type 2 adverse bleeding event that requires nonsurgical, medical intervention by a healthcare professional or leads to hospitalisation or increased level of care, should discontinue study drug but remain on study and continue to undergo protocol mandated evaluations and assessments. The participant should be monitored as frequently as clinically required for the particular bleeding event. At least weekly is recommended. The appropriateness of whether to re-challenge the participant with the study drug will be left to the investigator's clinical judgement but the long half-life of vorapaxar must be taken into account.

10.3.2.3 BARC Type 3 Bleeding

Participants who develop a BARC type 3a, 3b or 3c (intracranial or intraocular) bleeding event will have the study drug permanently discontinued. Participants experiencing BARC type 3a or 3b AEs must be followed regularly (at least 4-5 times per week is suggested) until resolution of the adverse event. Participants experiencing a BARC Type 3c event (intracranial or intraocular bleed) must be followed on a daily basis until the resolution of the event. The patient should remain on study and continue to undergo protocol-specified evaluations and assessments. A BARC type 3 event would trigger an 'out of session' meeting of the Data Safety Monitoring Board to review the event in an unblinded manner.

10.3.2.4 BARC Type 4 Bleeding

Any participant who is planning to undergo any planned surgical procedure 6 months after the planned randomisation should not be enrolled into the study. If there is a need for a participant to undergo an emergency CABG or any other surgical procedure during the course of the study, the study drug should be immediately and permanently discontinued. If deemed necessary, unblinding procedures could be initiated but attention to how best do this will be given to avoid site staff becoming aware of the treatment allocation.

It is important that the treating physician is informed that vorapaxar results in residual platelet aggregation activity 4 weeks after stopping and appropriate clinical decisions are made. There is no known antidote for vorapaxar. It is the investigator’s responsibility to inform the treating physician of this.

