3.3 Vorapaxar

Vorapaxar sulphate (Zontivity™) is a first in class, tricyclic himbacine-derived selective inhibitor of platelet aggregation mediated by PAR-1.

Vorapaxar has been developed in a number of primary and secondary care settings for cardiovascular diseases. In the setting of acute coronary syndromes vorapaxar did not affect a composite primary endpoint that included death, MI, stroke, recurrent ischemia or coronary revascularisation but did significantly

increase the risk of major bleeding including intracranial haemorrhage¹¹. In a further study that followed 26,449 patients with a history of MI, cerebral stroke or peripheral arterial disease, vorapaxar significantly reduced the risk of cardiovascular disease mortality and ischemic events among patients with stable atherosclerosis while also increasing the risk of moderate to severe bleeding including intracranial haemorrhage¹². This study identified the risk of severe bleeding among patients with a history of stroke – which would now be regarded as contraindicated for treatment with vorapaxar and therefore participation in this study. Importantly, the findings arose among a patient group who were also receiving standard secondary prophylaxis for CVD (88% receiving aspirin and 78% receiving thienopyridine) and so the effects reflect adjunctive use to already potent anti-thrombotic therapy. The hazard ratio (95% CI) for vorapaxar recipients relative to placebo recipients for the primary endpoint (fatal CV event, MI or stroke) was 0.87 (0.80-0.94; $p < 0.001$). A total of 2204 patients experienced a primary event over three years, 1028 (9.3%) vorapaxar recipients and 1176 (10.5%) of placebo recipients. Moderate or severe bleeding occurred in 4.2% of patients who received vorapaxar and 2.5% of patients who received placebo (HR, 1.66; 95% CI 1.43–1.93; $p < 0.001$).

Vorapaxar has now been licensed in the USA as secondary prophylaxis for patients with a history of MI or peripheral arterial disease except ischemic stroke.

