8.1 Vorapaxar

Vorapaxar sulphate is an oral competitive PAR-1 antagonist that inhibits thrombin-induced platelet aggregation. Vorapaxar is eliminated primarily by metabolism with contributions from CYP3A4 and CYP2J2. The primary route of elimination is through the faeces and to a lesser degree in urine. It has an effective half-life of 3-4 days and an apparent terminal elimination half-life of 8 days (range 5-13 days).

One vorapaxar sulphate encapsulated tablet (2.5mg) or matching placebo should be taken orally, once daily with or without food. A one month supply of vorapaxar or matching placebo will be provided at each dispensing visit (weeks 0, 4 and 8). Study drug will be dispensed from local pharmacies in a bottle containing a desiccant packet to protect the drug from moisture. The bottles must be stored at 20-25°C (68-77°F). Temperature monitoring logs will be kept at each pharmacy and checked during monitoring visits. All details regarding supply and dispensing of study treatment will be outlined in the MOOP.

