8.2 Prior and concomitant medications

Given the involvement of CYP3A4 and CYP2J2 in the metabolism of vorapaxar, participants with HIV infection whose ART therapy includes ritonavir or cobicistat boosted PIs or NNRTIs (apart from rilpivirine) will not be enrolled into the study. Vorapaxar can increase the risk of bleeding in proportion to a participant's underlying bleeding risk. To this end, participants who have a history of bleeding disorders, active bleeding or are planning to undergo an elective surgical procedure within the 6 month period following randomisation will be excluded from the study. Certain concomitant medications are also known to increase the risk of

bleeding. As such, participants taking anticoagulants, (e.g. heparin or warfarin), fibrinolytic therapy or chronic (more than 5 consecutive days) nonsteroidal anti-inflammatory drugs (NSAIDS) will also be excluded from the study. A list of medications to avoid will be listed in the MOOP.

If during the course of the study, a participant needs treatment with a potent CYP3A4 inhibitor or inducer or other medication listed above, study treatment must be discontinued immediately. In the case of a potent CYP3A4 inhibitor or inducer, where possible, an alternative treatment should be given to avoid participants coming off study medication unnecessarily. Study treatment should recommence as soon as clinically possible with the safety and well-being of the participant paramount. It is important that the treating physician is informed that vorapaxar results in residual platelet aggregation activity 4 weeks after stopping and appropriate clinical decisions are made. Whilst there is no known antidote for vorapaxar, monkey data suggest that platelet transfusions of sufficient quantity (a full pheresis pack or two) have the potential to transiently (a few hours) reverse the antiplatelet activity of vorapaxar. It is the investigator's responsibility to inform the treating physician of this.

In this protocol all concomitant medications including over the counter medicines and natural supplements will be recorded.

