11.6 Definition and reporting of an overdose

In previous studies, vorapaxar has been given in single doses up to 120mg and daily doses of 5mg for up to 4 weeks without identification of a specific risk or dose related adverse events. However, for the purposes of this study, an overdose of vorapaxar is defined as 3 doses (7.5mg) or more within 24 hours. Any overdose, whether or not associated with an adverse reaction, must be reported within 24 hours on the paper SAE form to the Kirby Institute and the participant monitored closely for signs and symptoms of adverse reactions and appropriate clinical care given

There is no known treatment to reverse the antiplatelet effect of vorapaxar. Dialysis or platelet infusion is not expected to be beneficial if bleeding occurs after an overdose. Monkey data suggest that platelet transfusions of sufficient quantity (a full pheresis pack or two) have the potential to transiently (a few hours) reverse the antiplatelet activity of vorapaxar. There is no standard test available to assess the risk of bleeding in case of an overdose.

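### The residual-effect message that investigators must pass to treating physicians is worded against the drug's stated action, and the platelet-transfusion statements are not consistent across sections

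*Protocol*

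**What the plan says.** Two sections of the protocol give the drug's action. Section 3.3 calls vorapaxar a "selective inhibitor of platelet aggregation mediated by PAR-1", and Section 8.1 calls it an "oral competitive PAR-1 antagonist that inhibits thrombin-induced platelet aggregation".

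Two sections tell the investigator what to pass on about the period after stopping. Section 8.2 deals with participants who come to need a medication that the trial prohibits, and it states: "It is important that the treating physician is informed that vorapaxar results in residual platelet aggregation activity 4 weeks after stopping". Section 10.3.2.4 deals with emergency bypass or other surgery during the study and uses the same words: "vorapaxar results in residual platelet aggregation activity 4 weeks after stopping". Both sections make passing this on a duty of the investigator. In Section 10.3.2.4 it is the investigator's "responsibility to inform the treating physician of this".

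Three sections address reversal:

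- Section 8.2 says that no antidote is known, then adds that on monkey data platelet transfusions of adequate size "have the potential to transiently (a few hours) reverse the antiplatelet activity of vorapaxar. It is the investigator's responsibility to inform the treating physician of" that finding.
- Section 10.3.2.4 says that no antidote is known and does not mention platelets.
- Section 11.6, on overdose, says that no treatment is known to reverse the effect and that "Dialysis or platelet infusion is not expected to be beneficial if bleeding occurs after an overdose". The next sentence says that, on monkey data, sufficient platelet transfusions "have the potential to transiently (a few hours) reverse the antiplatelet activity of vorapaxar".

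**The concern.** The residual-effect sentence is an instruction, not background. It tells the investigator what a physician outside the trial must know before surgery or before adding an interacting drug. That physician may not have the protocol and will usually be working with a blinded participant. Taken at face value, the sentence says that aggregation persists for four weeks, whereas the drug's stated action is to prevent it. The same wording stands in two sections, so correcting one leaves the other.

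The platelet statements raise a second, separate question. Depending on which section is open, a reader finds that platelets may help briefly, finds nothing about platelets, or finds both that they are not expected to help and that they may. Bleeding is the trial's main safety risk: Section 6.2.2 makes it a particular focus of the safety analyses, and Section 10.3.2 sets out how each bleeding type is to be managed.

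**Working it through.** No sample size, power or error rate is involved, so the check is a comparison of the texts.

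| Section | Setting | Drug's action, or what persists | Platelets | Duty to inform physician |
|---|---|---|---|---|
| 3.3 | Background | Inhibits aggregation | – | No |
| 8.1 | Drug description | Inhibits aggregation | – | No |
| 8.2 | Prohibited medication needed | Aggregation activity remains at 4 weeks | May reverse effect for a few hours (monkey data) | Yes |
| 10.3.2.4 | Surgery during the study | Aggregation activity remains at 4 weeks | Not mentioned | Yes |
| 11.6 | Overdose | – | Not expected to help; next sentence: may reverse effect for a few hours (monkey data) | No |

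**Step 1: the residual-effect sentence.** The third column shows the conflict. Sections 3.3 and 8.1 name inhibition. Sections 8.2 and 10.3.2.4 contain no word for inhibition in the sentence itself. Their context points the other way from the literal text: Section 8.2 says earlier that the drug can raise bleeding risk and speaks of its antiplatelet activity in the very next sentence, and Section 10.3.2.4 stands under a bleeding heading and follows with the remark on antidotes.

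**Step 2: plausibility.** Section 8.1 gives an effective half-life of 3–4 days and a terminal half-life of 8 days (range 5–13). Assuming single-exponential decay, the fraction of drug left after 4 × 7 = 28 days is 0.5^(28/h):

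- h = 8 days: 0.5^3.5 = 8.8%
- h = 5 days: 0.5^5.6 = 2.1%
- h = 13 days: 0.5^2.15 = 22.5%
- h = 3 to 4 days: 0.5^9.33 to 0.5^7 = 0.2% to 0.8%

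On the terminal half-life some drug is still present at four weeks, which fits persisting inhibition as the intended meaning. On the effective half-life almost none is left, and the protocol does not relate drug level to platelet effect. The check is consistent with that reading but does not prove it.

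**Step 3: the platelet statements.** The direct tension is between two adjacent sentences of Section 11.6, and between the first of these and Section 8.2. Section 10.3.2.4 conflicts with neither; it leaves the subject out. So Section 8.2 gives one statement, Section 10.3.2.4 gives none, and Section 11.6 gives two that do not sit together.

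**Step 4: who is covered.** The duty to inform is attached to starting a prohibited medication (Section 8.2) and to surgery (Section 10.3.2.4). Sections 10.3.2.2 and 10.3.2.3, on BARC type 2 and type 3 bleeding, do not contain the message. Section 11.6 applies to overdose, defined there as three or more doses (7.5 mg) within 24 hours.

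**The case against.** The strongest reply is that nobody would be misled. The protocol identifies the drug as an antiplatelet agent throughout, the sentence appears among bleeding warnings, and a remark about antidotes makes sense only if inhibition persists. A reader might infer that the protocol asserts a reversed drug effect, but the context does not support that; the sentence looks like a slip in wording. This part of the reply stands. It does not remove the case for correction, because a required safety message should not rely on its recipient to repair it.

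A reader might also infer that the information investigators must pass on contradicts itself about platelets. It does not. The duty appears only in Sections 8.2 and 10.3.2.4, both of which say that no antidote is known, and the second is merely less complete. The sentence expecting no benefit is in Section 11.6, is limited to overdose, and carries no duty to inform.

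It can further be said that a short-lived signal in monkeys is compatible with no expected clinical benefit, so that Section 11.6 is in tension rather than in flat contradiction. That is fair as far as it goes. But the section does not say so, and the reader is left to supply the reconciliation.

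Finally, the occasions should be few. There are 60 participants randomised 1:1, so about half receive placebo. Section 7.1 excludes intended surgery within six months, recent bleeding disorders, and current aspirin or anticoagulant use. Section 11.7 requires code-break access around the clock. Section 8.3 points to the product information and Investigator Brochure, at least for medications to avoid. All of this limits the likely consequence, and none of it corrects the text.

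**Conclusion.** Wrong as written, at low severity. One sentence, repeated in Sections 8.2 and 10.3.2.4, is at odds with the drug's action in Sections 3.3 and 8.1. The platelet statements in Sections 8.2, 10.3.2.4 and 11.6 are not aligned, and the only direct conflict involves Section 11.6.

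A reader might infer that every participant with a bleed is exposed to the faulty message. The documents tie it to prohibited medication and surgery, so that reach is not supported, and the number affected cannot be derived. Nor do the documents show that any physician would act wrongly, or say in what form the message is given. Randomisation, endpoints, sample size and efficacy analyses are untouched.

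The conclusion rests on the wording alone. The view that persisting inhibition was meant is an inference from context, and the documents do not settle which platelet statement is right.

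**What to change.** Reconcile the residual-effect sentence in Sections 8.2 and 10.3.2.4 with Sections 3.3 and 8.1, changing both places together. Reconcile the platelet-transfusion statements in Sections 8.2, 10.3.2.4 and 11.6 so that they carry one consistent message, and make clear whether any difference for overdose is intended. The clinical content is for the sponsor's medical team; no clinical rule is proposed here. The cost is a few lines of protocol wording and a memo to sites, with no change to the design, the data collected or the SAP.

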10.3.2.5 BARC Type 5 Bleeding

If any participant suffers a fatal bleed the blind for that participant will be broken. If the participant was taking vorapaxar at the time of the event, the trial will be temporarily stopped whilst the Data Safety Monitoring Board (DSMB) reviews the event in light of other clinical safety information for the study. Please see section 18.0 for details on DSMB.

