8.0 Treatment of participants

Eligible participants will be randomised in equal proportions to receive either:

- I. vorapaxar sulphate (2.5mg qd) for 12 weeks
- II. matched placebo for 12 weeks

All participants will stop study treatment at the week 12 visit and then be seen for a final visit at week 18. All participants will stop taking the study medication at the week 12 visit, even if having undergone a period of study drug interruption. The treatment period will not be extended to account for the missing days.

Randomisation will be conducted via the electronic case report form. Specific details regarding randomisation will be provided in the study Manual of Operations (MOOP). Randomisation will be stratified by centre on a 1:1 basis.

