11.3.1 Reporting of SUSARs

The Project Team in collaboration with the Medical Officer will review and identify all serious events which fit the criteria of a SUSAR and require expedited reporting to relevant parties. The event will be designated as unexpected if it is not reported in the Investigator Brochure or Product Information or if the event is of greater frequency, specificity or severity.

The Sponsor must expedite the reporting of all suspected unexpected and certainly, probably, possibly, or of undetermined relationship to the study drug to all concerned investigators/institutions, IRB/IEC/s, and regulatory authorities within 7 days if it is life-threatening or fatal or within 15 days if not. Reports must comply with the applicable regulatory requirements and ICH Guideline for Clinical Safety Data Management: Definitions and Standards for Expedited Reporting.

Researchers must inform the IRB/IEC and regulatory authorities of all serious or unexpected AEs that occur during the study which may affect the conduct of the study or the safety of the participants and/or their willingness to continue participation in the study.

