18.0 Data Safety and Monitoring Board (DSMB)

The DSMB will be accountable to the PSC and will undertake independent review of protocol-specified and ad hoc interim analyses if required. The DSMB will be composed of individuals neither directly associated with the study nor employees of any of the organisations responsible for the conduct of the research. The study biostatistician will be an ex officio member of the DSMB. The primary focus of the reviews undertaken by the DSMB will be safety. The first scheduled review will take place after 20 patients have completed 6 weeks of treatment with further reviews scheduled every 8 weeks thereafter. For ad hoc reviews an interim analysis would be prompted when four (4) BARC type 2 events or one (1) BARC type 3 event are reported. During the ad hoc review and until the PSC has received and acted upon a DSMB recommendation, patient recruitment will be paused but randomised patients will continue study treatment. The terms of reference and operating

guidelines of the DSMB will be drafted by the study biostatistician (as documents separate to the Protocol) and finalised in collaboration with the DSMB prior to the commencement of the study.

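### A fatal bleed that begins after a participant has stopped vorapaxar has no explicit event-triggered DSMB review or trial stop, although the protocol states residual activity 4 weeks after stopping

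*Protocol*

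**What the plan says.** The rules on serious bleeding are split between Protocol sections 10.3.2 and 18.0.

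- **Fatal bleed (10.3.2.5).** The participant is unblinded in every case. The next step is conditional: "If the participant was taking vorapaxar at the time of the event, the trial will be temporarily stopped" while the DSMB reviews the event. The section then refers the reader to 18.0.
- **Type 3 bleed (10.3.2.3).** "A BARC type 3 event would trigger an 'out of session' meeting of the Data Safety Monitoring Board", with the data unblinded. Nothing is said about whether the participant is still dosing.
- **Ad hoc triggers (18.0).** An interim analysis is prompted when "four (4) BARC type 2 events or one (1) BARC type 3 event are reported". Type 5 is not in the list. During an ad hoc review recruitment pauses, but participants already randomised keep taking study treatment.
- **Scheduled reviews (18.0).** The first follows once 20 patients have completed 6 weeks of treatment, with "further reviews scheduled every 8 weeks thereafter".
- **Off-drug time.** "All participants will stop study treatment at the week 12 visit" (8.0), and follow-up runs to week 18. A participant with a type 2 bleed that needs medical intervention or a higher level of care "should discontinue study drug but remain on study" (10.3.2.2). Emergency surgery (10.3.2.4) and the need for a prohibited medicine (8.2) also end dosing at once.
- **Persistence of effect.** Sections 8.2 and 10.3.2.4 both tell the investigator to warn the treating physician of residual activity 4 weeks after stopping. On re-challenge after a type 2 bleed, 10.3.2.2 says that "the long half-life of vorapaxar must be taken into account".

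The SAP contains no monitoring or stopping rules.

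**The concern.** Of the bleeding categories for which the protocol mandates a DSMB response, type 5 is the only one whose response depends on current dosing. For a short-acting drug that could be a fair proxy for causal relevance. For this drug it is not, because the protocol elsewhere treats a person who has recently stopped as still at pharmacological risk.

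Being off drug is also a planned state, and several routes into it coincide with raised bleeding risk: a recent type 2 bleed, emergency surgery, or starting an anticoagulant. A first type 2 bleed would not bring the DSMB in by itself, since four are needed.

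Patient safety is what is at stake. If such a death occurred, other participants could continue dosing and recruitment could continue without any explicit rule sending the case promptly to the DSMB.

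**Working it through.** The protocol gives no figure to reproduce. The check sets the rules side by side, then asks how much time and residual drug the on-drug condition leaves out.

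**Step 1. Compare the mandated responses.**

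| Event | Depends on current dosing? | Mandated response |
|---|---|---|
| One type 3 bleed | No | Out-of-session unblinded DSMB meeting (10.3.2.3); ad hoc review with recruitment paused and treatment continuing (18.0) |
| Type 5 bleed, taking vorapaxar | Yes, met | Unblinding, temporary trial stop, DSMB review (10.3.2.5) |
| Type 5 bleed, vorapaxar stopped, not reported as type 3 | Yes, not met | Unblinding only; no event trigger in 10.3.2.5 or 18.0 |

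The third row is the gap.

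**Step 2. Off-drug time by design.** Dosing ends at week 12 and the final visit is at week 18 (8.0). 18 − 12 = 6 weeks, and 6/18 = 33% of nominal follow-up. The literal condition cannot be met in that time. This is calendar time and says nothing about how likely a fatal bleed is.

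**Step 3. Residual drug.** Section 8.1 gives an effective half-life of 3–4 days and a terminal half-life of 8 days (range 5–13). Assuming simple first-order decay, the fraction left after d days is 0.5^(d/h), where h is the half-life.

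| h (days) | 28 days | 42 days |
|---|---|---|
| 3 (effective) | 0.16% | 0.01% |
| 4 (effective) | 0.78% | 0.07% |
| 5 (terminal, low) | 2.1% | 0.3% |
| 8 (terminal) | 8.8% | 2.6% |
| 13 (terminal, high) | 22.5% | 10.7% |

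For example, 0.5^(28/8) = 0.5^3.5 = 8.8%. On the effective half-life less than 1% remains at 4 weeks, so the decay figures alone do not make the case. It rests on the protocol's own 4-week statement, which does not say that activity ends there.

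**Step 4. What remains when the condition fails.**

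- *Scheduled DSMB review:* at most 8 weeks away once reviews have begun. Before the first review the wait depends on accrual and cannot be bounded from the documents.
- *Discretionary ad hoc review:* allowed by 18.0, but not required for a type 5 event.
- *SAE report:* within 24 working hours (11.2.1), with review by the project team and Medical Officer. The DSMB is not named as a recipient.
- *SUSAR report:* "within 7 days if it is life-threatening or fatal or within 15 days if not" to investigators, ethics committees and regulators (11.3.1). Again the DSMB is not named. Bleeding, including intracerebral bleeding, is a known reaction (10.3.1), so a fatal bleed may or may not be judged unexpected.

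None of these is an explicit, immediate DSMB step.

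**The case against.** Four arguments on the other side have weight.

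1. **Overlap with type 3.** Appendix 2 excludes types 3, 4 and 5 from type 2, but does not exclude fatal events from type 3. Type 3c covers intracranial haemorrhage and allows confirmation by autopsy, so it contemplates deaths. Types 3a and 3b cover any transfusion with overt bleeding, surgical control and vasoactive agents. Many fatal bleeds would therefore engage the unconditional type 3 trigger, on or off drug. This stands and shrinks the gap considerably. It does not close it: type 5a is a clinically suspected fatal bleed without autopsy or imaging confirmation, and a sudden death of that kind could have no type 3 report.
2. **The condition may mean allocation.** It directly follows the unblinding sentence, and section 11.7 speaks loosely of the treatment a participant is on when it means the allocated arm. This is plausible, but the reference to the time of the event strains it, and a safety rule should not need interpretation. The event is most naturally the bleed, so someone who bled on drug, stopped and died later is covered.
3. **The on-drug response is the stronger one.** A trial stop goes further than a recruitment pause, and confining it to vorapaxar recipients is sensible. That stands, and the remedy keeps the restriction.
4. **Unseen documents.** The DSMB terms of reference are separate and may already cover type 5.

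A reader might infer that an off-drug fatal bleed would receive no mandated review at all. The documents do not support that: section 18.0 requires scheduled reviews whose primary focus is safety. Nor do they support a claim that type 5 is handled more weakly than type 3 in general, since unblinding is unconditional and the on-drug response is more severe.

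**Conclusion.** The point holds in a narrow form. On the literal wording, a fatal bleed that begins after a vorapaxar participant has stopped drug, and that was not also reported as type 3, triggers unblinding but no explicit DSMB review and no trial stop. That is inconsistent with the protocol's own account of persisting activity.

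No risk can be attached to it. The documents give no fatal-bleed rate for this population, the trial has 60 participants, and people at high bleeding risk are excluded. In time, the condition leaves out 6 of 18 nominal weeks for everyone, plus any earlier off-drug period. If no other safeguard acted, the delay to DSMB review could reach 8 weeks once scheduled reviews are running.

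The conclusion assumes that the condition refers to current dosing and that the DSMB terms of reference do not already list type 5. If either assumption fails, the gap shrinks or disappears and only a clarification is needed. The severity is minor, and efficacy conclusions are untouched.

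**What to change.** 1. In section 18.0, add *one BARC type 5 event, whatever the current drug status* to the ad hoc triggers. State that where 10.3.2.5 also applies, its trial stop takes precedence over the rule that randomised participants continue treatment.
2. In section 10.3.2.5, replace the on-drug condition with *was allocated to vorapaxar and took a dose within at least the 4 weeks before bleed onset*. A simpler alternative is *was allocated to and had received vorapaxar*, applied through week 18. It needs no last-dose date and covers the whole off-drug phase.
3. Carry the same wording into the DSMB terms of reference if they repeat the current rule.

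The cost is a wording amendment, with no new data, visits or sample-size change. The one downside is a possible extra temporary pause after a rare event.
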